2.8 Risks/Benefits of Roxadustat Treatment

The primary benefit of roxadustat is the correction of anemia, including the relief of associated signs and symptoms and an increased QOL. Roxadustat is expected to be at least as safe as ESAs, and the current data suggest that cardiovascular risk may be lower than with ESAs.

An established dose adjustment algorithm will be used during the study to titrate roxadustat doses to enable subjects to achieve and maintain optimal Hb levels, while closely monitoring the rate of rise of Hb levels. Roxadustat doses may be held and/or the use of therapeutic phlebotomy is allowed in the event of excessive hematopoiesis.

The safety of treatment with roxadustat and placebo will be carefully monitored. Adverse and serious adverse events, and laboratory parameters including CBC, electrolytes, liver enzymes, CPK, and iron indices, will be closely monitored. An independent expert panel will assess and adjudicate prespecified cardiovascular, cerebrovascular, and thromboembolic events. In addition, an independent Data and Safety Monitoring Board (DSMB) will perform regular, periodic assessments of safety data to detect any potential safety signals that may arise during the study and advise the Sponsor accordingly.

Based on the clinical and nonclinical experimental results to date, it is anticipated that orally administered roxadustat will be comparable in efficacy to marketed parenteral ESA products in the treatment of anemia of CKD, with an acceptable safety profile. Roxadustat may offer a valuable alternative to the current treatment options in the management of anemia of CKD.

3 OBJECTIVES

3.1 Primary Objectives

The primary objectives of this study are to:

- Evaluate the efficacy of roxadustat for the treatment of anemia (correction and maintenance of Hb) in CKD subjects not on dialysis.
- Evaluate the safety of roxadustat administered over a minimum of 52 weeks of treatment.

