4 STUDY DESIGN

4.1 Description of the Study

This is a Phase 3, multicenter, randomized, double-blind, placebo-controlled study to evaluate the safety and efficacy of roxadustat in the treatment of anemic subjects with Stage 3, 4 or 5 CKD who are not on dialysis. This study is planned to recruit up to 1200 subjects from approximately 200 study centers worldwide.

This study will consist of three study periods as follows:

- Screening Period: Up to 6 weeks
- Treatment Period: Treatment duration is variable for individual subjects. In order to complete the Treatment Period simultaneously for all study subjects, the minimum treatment duration may be less than 52 weeks, with a maximum treatment duration of up to 3 years after the last subject is randomized.
- Post-treatment Follow-Up Period*: 4 weeks
(*or enroll into an Open Label Extension study)

Refer to Appendix 3 for a diagrammatic representation of the study schema.

Following the Screening Period, subjects will be randomized in a 2:1 ratio to receive roxadustat (approximately 800 subjects) or placebo (approximately 400 subjects). Dosing will be TIW throughout the study, except in subjects who have already converted to BIW or QW dosing regimens as a result of being enrolled under previous Study FGCL-4592-060 protocol versions. Starting doses of , respectively.

Table 1. Treatment Arms

Treatment Arms	Correction	Maintenance	n (FG-4592)	n (Placebo)
1A	TIW	QW	100 ^a	0
1P	TIW	QW	0	50 ^a
2A	TIW	BIW	100	0
2P	TIW	BIW	0	50
3A	TIW	TIW	100	0
3P	TIW	TIW	0	50

Abbreviations: A = active control; BIW = twice a week; n = number of subjects; P = placebo; TIW = three times a week; QW = once a week.

^a These numbers are based on a sample size of 450 and will increase if the overall sample size increases.

The initial study drug dose (per dose amount) is based on a tiered, weight-based dosing scheme shown in Table 2.

Table 2. Initial Study Drug (FG-4592 or Placebo) Dosing

Study Drug (Dose Frequency)	Low Weight (<70 kg)	Medium Weight (70 to 100 kg)	High Weight (>100 kg)
FG-4592/Placebo (TIW)	70 mg	100 mg	120 mg

Abbreviations: TIW = three times a week; QW = once a week.

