8 ENDPOINTS AND ASSESSMENTS

8.1 Primary Efficacy Endpoint

There are two separate regionally-based primary efficacy endpoints in this study depending upon whether the data are being filed to support submission to the US FDA or to Ex-US health authorities, such as the European EMA.

The **primary endpoint for the US (FDA)** submission is defined as the change in Hb from baseline to the average level during the evaluation period (defined as Week 28 until Week 52).

The **primary endpoint for the Ex-US** submission is defined as the proportion of subjects who achieve a Hb response at two consecutive visits during the first 24 weeks of treatment, without rescue therapy (ie, RBC transfusion, ESA, or IV iron)

A Hb response is defined, using central laboratory values, as the following:

- Hemoglobin ≥ 11 g/dL and Hb increase from baseline by ≥ 1 g/dL in subjects with baseline Hb > 8 g/dL, or
- An increase in Hb by ≥ 2 g/dL in subjects with baseline Hb ≤ 8.0 g/dL

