9.4.3.1 Primary Efficacy Analysis

The primary efficacy endpoint will be analyzed using the ITT population as the primary analysis population and PPS population as a supportive analysis population.

For US (FDA) Submission

The primary efficacy endpoint for the US (FDA) submission is the Hb CFB to the average level during the evaluation period, defined as Weeks 28 to 52.

The planned treatment duration is at least 52 weeks. The rationale for choosing the specified evaluation period as the primary endpoint for US (FDA) submission is that one would expect to have achieved Hb correction by Week 28, and averaging it to Week 52 would be an accurate reflection of a longer term therapeutic effect of roxadustat.

The hypothesis to be tested for the primary efficacy analysis is:

H_0 : Hb CFB to the average of Weeks 28 to 52 in the roxadustat group = Hb CFB to the average of Weeks 28 to 52 in the placebo group

Versus

H_1 : Hb CFB to the average of Weeks 28 to 52 in the roxadustat group = Hb CFB to the average of Weeks 28 to 52 in the placebo group

A Multiple Imputation Analysis of Covariance model (MI ANCOVA) will be used to compare the roxadustat and pooled placebo groups in a fixed sequence procedure: 1) pooled roxadustat (TIW+BIW+QW) vs. pooled placebo, 2) roxadustat TIW vs. pooled placebo, 3) roxadustat BIW vs. pooled placebo, 4) roxadustat QW vs. pooled placebo. The latter are being performed to test the BIW and QW maintenance dosing frequencies that are enrolled from earlier versions of the protocol. If a null hypothesis is rejected, the claim of the tested roxadustat regimen over placebo will be declared successful and the test will progress to the next comparison in sequence.

H_0 will be tested at the two-sided alpha = 0.05 level of significance and will be rejected if the $p < 0.05$ from the test.

Hemoglobin values under the influence of a rescue therapy will not be censored in the primary analysis. The model will contain terms for treatment arm, baseline measurement, visit, visit by treatment arm, and other randomization stratification factors. The primary efficacy analysis will be based on the estimated difference in the overall mean effect between the two treatment groups throughout the evaluation period based on the MI ANCOVA model.

For Ex-US Submission

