12.2.2.1 Timing and Extent of Missing Data

To assess the potential effect of missing data on the estimate of treatment effect, subjects will be classified as full data or missing data cases. Patterns of missing data will be based on non-missing hemoglobin values in the evaluation period.

- Full data cases are defined as subjects without non-missing hemoglobin for all scheduled weeks of the evaluation period.
- Missing data cases are defined as subjects with a missing hemoglobin value (s) on at least one scheduled assessment in of the evaluation period. The missing data cases are further grouped into intermittent missing and monotone missing cases.

- Intermittent missing hemoglobin cases are defined as subjects with a missing hemoglobin value for at least one scheduled assessment in the evaluation period but not on consecutive scheduled assessments up to the end of evaluation period.
- Monotone missing hemoglobin cases are defined as subjects who have missing Hb values in consecutive scheduled Hb assessments with missing hemoglobin up to the end of evaluation period. A subject who is a monotone missing case could have intermittent missing hemoglobin prior to the ending week.

Subjects will be grouped as follows:

- Full data cases
- Intermittent missing data cases
- Monotone missing data cases

Should the incidence of monotone missing data cases and intermittent missing data cases be relatively small (e.g., <xx%), then those cases will be combined so that the groups are full data cases and missing data cases. The summary of missing pattern in evaluation period will be presented in a table.

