12.2.2.4 PMM – Baseline Carried Forward (Roxadustat Only and Both Groups)

The analysis is the same as PMM – Last Mean Carried Forward except imputing the missing data. The imputation data will be generated similarly as last mean carried forward method described above but instead of using post-baseline observed data, only baseline data will be used. The similar analyses will be conduct in two scenarios.

- The baseline carried forward imputation will be performed for the roxadustat treatment group only, while for active control group, the imputation data will be generated using the last mean carried forward described above.
- The baseline carried forward imputation will be performed for the both treatment groups.

Similarly, the Rubin's method will be then used to combine the estimates and the differences between the least square mean differences between the two treatment groups from each of the ANCOVA analysis. This sensitivity analysis will be performed for U.S. primary endpoints only.

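### The safety objective and Protocol 9.4.3.1 promise at least 52 weeks of treatment, the current design does not, and the SAP's pattern-mixture analyses do not separate common-end-date stops from dropout

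*Protocol*

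**What the plan says.** On duration, the current text says two things. The synopsis, Protocol 3.1 and SAP 2 set the primary safety objective over at least 52 weeks: "Evaluate the safety of roxadustat administered over a minimum of 52 weeks of treatment". Protocol 9.4.3.1 adds: "The planned treatment duration is at least 52 weeks". The design text in the synopsis, Protocol 4.1 and 4.5.1 and SAP 3 gives a different rule. "In order to complete the Treatment Period simultaneously for all study subjects", it says, "the minimum treatment duration may be less than 52 weeks". That text sets an upper limit of 3 years after the last randomisation and no lower limit.

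The US primary endpoint averages Hb over Weeks 28 to 52. In SAP 12.1, trailing missing Hb is multiply imputed to the end of that period, separately by treatment group. SAP 12.2.1 adds an MMRM.

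The pattern-mixture models in SAP 12.2.2 then test departures from MAR. Section 12.2.2.1 classifies by missingness alone: "Monotone missing hemoglobin cases are defined as subjects who have missing Hb values in consecutive scheduled Hb assessments", running to the end of the evaluation period. The trailing values are imputed from the last own-arm mean (12.2.2.3), from baseline (12.2.2.4) or from the placebo distribution (12.2.2.5). In one version, "The baseline carried forward imputation will be performed for the roxadustat treatment group only". None of these rules uses the reason for the missing value. The synopsis and Protocol 7.1.2.6 do draw that line: a non-completer is a subject who stops prematurely.

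**The concern.** Two live statements about minimum duration cannot both describe the same trial, and one of them is a primary objective. The update looks incomplete. SAP 12.1 repeats the rationale of Protocol 9.4.3.1 but omits its sentence on planned duration, and the protocol's summary of changes removes a secondary endpoint because treatment duration had become variable.

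The second issue follows from the first. A late-randomised subject who is doing well on roxadustat can reach the common end date before Week 52. That stop is set by the calendar and says nothing about the subject's Hb. Under SAP 12.2.2 the subject would be imputed as if the drug effect had been lost. The stress tests are meant to show how far the result depends on what happened to people who dropped out. If planned truncation is mixed in, a shift in the estimate cannot be read that way.

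**Working it through.** **Step 1. Duration statements side by side**

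| Place | Minimum treatment duration |
|---|---|
| Synopsis objectives, Protocol 3.1, SAP 2 | 52 weeks |
| Protocol 9.4.3.1 | at least 52 weeks (planned) |
| Synopsis design, Protocol 4.1 and 4.5.1, SAP 3 | may be under 52 weeks, no floor |
| SAP 12.1 (same rationale as 9.4.3.1) | sentence absent |

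**Step 2. The plan's own power figure**

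Inputs (Protocol 9.1, SAP 5.1): 300 vs 150 subjects, SD 1.2 g/dL, two-sided 0.05. SE = 1.2 × √(1/300 + 1/150) = 1.2 × 0.1 = 0.12 g/dL.

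- Difference 1 g/dL (protocol): 1/0.12 = 8.33, power above 99.99%.
- Difference 0.75 g/dL (SAP): 0.75/0.12 = 6.25, power 99.999%.

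Both reproduce the stated figure of more than 99%.

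**Step 3. One subject through the rules**

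Take a roxadustat subject whose common end date falls at Week 36. Visits are every 4 weeks, so Weeks 28, 32 and 36 are observed and Weeks 40, 44, 48 and 52 are not.

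- Primary MI ANCOVA: the four values are imputed from the roxadustat arm (MAR).
- MMRM: they are left missing and handled under MAR.
- Pattern-mixture models: the subject is a monotone missing case. The four values come from the last own-arm mean, from baseline or from placebo, depending on the model.

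**Step 4. Size of the pull toward zero**

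Let f be the share of roxadustat subjects stopped by the common end date before Week 52, m the share of the seven evaluation visits (28, 32, 36, 40, 44, 48, 52) lost, and δ the true difference. If the lost visits take the control mean (jump-to-control), or baseline with no mean change on placebo, then

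loss ≈ f × m × δ.

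m is 7/7 for a stop by Week 24, 4/7 at Week 36, 2/7 at Week 44 and 1/7 at Week 48. Under SAP 17.1 the Week 28 window opens at Day 197 − 14 = 183 (Week 26) and the end-of-treatment value is mapped to the closest visit. So only subjects stopped before about Week 26 lose all seven.

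The documents do not give f, so the table shows an assumed range. Loss in g/dL for δ = 0.75:

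| f | Stop by Week 24 | Stop at Week 36 | Stop at Week 44 |
|---|---|---|---|
| 5% | 0.038 | 0.021 | 0.011 |
| 10% | 0.075 | 0.043 | 0.021 |
| 20% | 0.150 | 0.086 | 0.043 |
| 30% | 0.225 | 0.129 | 0.064 |

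For δ = 1.0, multiply by 4/3. The formula ignores carry-over from a subject's earlier values under jump-to-control.

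**Step 5. Does it change a conclusion?**

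In the most extreme cell the estimate is 0.75 − 0.225 = 0.525 g/dL. Then 0.525/0.12 = 4.375, and power at N = 450 is still 99.2%.

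**Step 6. When the loss is zero**

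If the common end date is at least 52 weeks after the last randomisation, every subject has Week 52 available and f = 0.

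**The case against.** The strongest reply is that this is a wording conflict with little behind it. Most of the points about size are correct.

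- The primary MI already imputes these stops within arm under MAR, which suits calendar truncation. Of the eight rows in SAP Table 4, four (MI ANCOVA and MMRM, with and without rescue censoring) are MAR analyses. Last-mean-carried-forward also stays within arm. Only baseline-carried-forward and jump-to-control are clearly affected, and they are meant to be harsh.
- The number affected may be zero. The summary of changes says the amendment lets the study continue, and the design allows up to 3 years after the last randomisation.
- The SAP never calls these subjects dropouts. The word scheduled in 12.2.2.1 could be read to exclude visits after a subject's own end of treatment. However, SAP 12.1 imputes through the end of the evaluation period and no exclusion is stated, so that reading needs to be written down.
- Safety reporting already allows for unequal follow-up. SAP 13.1.1 counts events from first dose to 28 days after last dose, so no event percentage is defined over 52 weeks. SAP 13.1.2 adds exposure-adjusted rates and cumulative incidence at 6, 12, 18 and 24 months. SAP 12.3 uses Kaplan-Meier for rescue and transfusion proportions.

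Two things remain: the conflict in a primary objective, and stress tests that cannot be read as tests of dropout if calendar stops are among the cases. A harsher stress test is not more informative when part of the penalty falls on people who did not drop out.

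**Conclusion.** The contradiction is in current text and must be reconciled. The pattern-mixture consequence follows from the SAP's rules as written, but it is confined to the sensitivity analyses. Its size is unknown: about 0.01 g/dL at f = 5% with a stop at Week 44, 0.075 g/dL at f = 10% with a stop by Week 24 (both for δ = 0.75), and zero if the end date is at least 52 weeks after the last randomisation. These figures rest on assumed f and stop times and on the approximation in Step 4.

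A reader might infer three stronger claims that the documents do not support.

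- That the primary result or the power is compromised. Own-arm imputation under MAR handles these stops, and the power figures reproduce.
- That the trial can say nothing about safety at 52 weeks. The 12-month cumulative incidence and the exposure-adjusted rates use each subject's available follow-up.
- That a sizeable share was cut off before Week 28. Enrolment duration and end date are not given. If one assumes uniform enrolment over 156 weeks and an end date 26 weeks after the last randomisation, the share is (28 − 26)/156 = 1.3%, before the visit windows reduce it further.

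**What to change.** 1. Reconcile the duration statements. If the variable-duration design stands, reword the objective in the synopsis, Protocol 3.1 and SAP 2 to safety over treatment of variable duration, and delete the sentence on planned duration in Protocol 9.4.3.1, as SAP 12.1 already does.
2. In SAP 12.2.2, make treatment ended at the common end date a separate pattern, flagged from that date and the disposition data. Impute it under own-arm MAR in every pattern-mixture model. Apply last-mean, baseline-carried-forward and jump-to-control only to premature discontinuations. Report the number in each pattern by arm, so that f is known.

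A restricted 52-week safety set is not needed, because SAP 13.1.2 already covers unequal follow-up.

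The cost is a few lines of text and one flag from data already collected, settled before database lock. The stress tests become slightly less conservative.

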3.2 Secondary Objectives

The secondary objectives in this study are to:

- Evaluate the effect of roxadustat in CKD anemia on:
 - Serum lipid parameters
 - HRQoL
 - Blood pressure
 - The need for anemia rescue therapy: red blood cell (RBC) transfusion, or ESA, or intravenous (IV) iron
 - Time to achieve Hb response

4 STUDY DESIGN

4.1 Description of the Study

This is a Phase 3, multicenter, randomized, double-blind, placebo-controlled study to evaluate the safety and efficacy of roxadustat in the treatment of anemic subjects with Stage 3, 4 or 5 CKD who are not on dialysis. This study is planned to recruit up to 1200 subjects from approximately 200 study centers worldwide.

This study will consist of three study periods as follows:

- Screening Period: Up to 6 weeks
- Treatment Period: Treatment duration is variable for individual subjects. In order to complete the Treatment Period simultaneously for all study subjects, the minimum treatment duration may be less than 52 weeks, with a maximum treatment duration of up to 3 years after the last subject is randomized.
- Post-treatment Follow-Up Period*: 4 weeks
(*or enroll into an Open Label Extension study)

Refer to Appendix 3 for a diagrammatic representation of the study schema.

Following the Screening Period, subjects will be randomized in a 2:1 ratio to receive roxadustat (approximately 800 subjects) or placebo (approximately 400 subjects). Dosing will be TIW throughout the study, except in subjects who have already converted to BIW or QW dosing regimens as a result of being enrolled under previous Study FGCL-4592-060 protocol versions. Starting doses of , respectively.

Table 1. Treatment Arms

Treatment Arms	Correction	Maintenance	n (FG-4592)	n (Placebo)
1A	TIW	QW	100 ^a	0
1P	TIW	QW	0	50 ^a
2A	TIW	BIW	100	0
2P	TIW	BIW	0	50
3A	TIW	TIW	100	0
3P	TIW	TIW	0	50

Abbreviations: A = active control; BIW = twice a week; n = number of subjects; P = placebo; TIW = three times a week; QW = once a week.

^a These numbers are based on a sample size of 450 and will increase if the overall sample size increases.

The initial study drug dose (per dose amount) is based on a tiered, weight-based dosing scheme shown in Table 2.

Table 2. Initial Study Drug (FG-4592 or Placebo) Dosing

Study Drug (Dose Frequency)	Low Weight (<70 kg)	Medium Weight (70 to 100 kg)	High Weight (>100 kg)
FG-4592/Placebo (TIW)	70 mg	100 mg	120 mg

Abbreviations: TIW = three times a week; QW = once a week.

Study drug will be dose adjusted according to anemia correction guidelines until subjects achieve a Hb value of ≥ 11 g/dL and ≥ 1 g/dL increase from baseline by central lab. Once these criteria are met, subjects will enter into the maintenance phase of anemia treatment and will be dose-adjusted according to maintenance guidelines (Section 4.5.2, Appendix 1).

Study drug dose will remain constant during the first 4 weeks of the Treatment Period, unless a dose reduction is required for excessive hematopoiesis. Dose adjustments are permitted starting at Week 4, and at intervals of every 4 weeks thereafter.

4.2 Randomization and Treatment Assignment

Up to 1200 planned subjects will be randomized to receive either roxadustat or placebo in a double-blind manner, resulting in approximately 800 subjects receiving roxadustat and approximately 400 subjects receiving placebo.

Randomization is stratified by the following factors:

- Screening Hb values (≤ 8 g/dL vs > 8 g/dL)
- History of cardiovascular, cerebrovascular or thromboembolic diseases (Yes vs No)
- eGFR (< 30 mL/min/1.73 m² vs ≥ 30 mL/min/1.73 m²)
- Geographic region (US vs Ex-US).

Randomization schedules will be prospectively prepared. Automated randomization and treatment assignments will be provided by an Interactive Response System (IWRS).

4.3 Replacement of Subjects

Subjects who drop out prematurely will not be replaced in the study.

4.4 Blinding

This is a double-blind, placebo-controlled study. The Investigator, study site staff, subject, and the Sponsor and designees, are blinded to study drug assignment, but not to the dose. Additionally, all efforts should be made to keep subjects blinded to study Hb values.

4.4.1 Maintenance of Blinding

Neither the subjects nor the Investigators and their staff can distinguish the roxadustat tablets from the matching placebo tablets. Both will be identical in appearance, packaging, and labeling in order to maintain the blind.

4.4.2 Planned and Unplanned Unblinding of Treatment Assignment

Treatment assignments will be unblinded after the completion of the study.

Any intentional or unintentional breaking of the blind should be reported and documented. Breaking the blind (for a single subject) should be considered only when knowledge of the treatment assignment is deemed essential by the Investigator for the subject's care. Unplanned unblinding will result in the discontinuation of subject participation from the study. When possible and appropriate the blind will be maintained for Sponsor personnel responsible for analysis and interpretation of results at the study's conclusion.

